7.8 Early Termination Visit

7.8.1 Withdrawal of consent

Study subjects may withdraw voluntarily from participation in the study at any time. Study subjects may also withdraw voluntarily from receiving the study intervention for any reason. If a study subject withdraws or is discontinued from the study at any time prior to completion of the study, the study subject will be encouraged to complete safety follow-up visits and allow adverse event monitoring and reporting. All data collected up until date of withdrawal will be retained for study analysis.

7.8.2 Early termination for re-transplantation between study day 30 and 365

Subjects retransplanted after 30 days of randomization will be withdrawn from the study and receive standard care at that point since prolonged drug continuation can potentially impact the study outcomes. Subjects that require re-transplantation of their liver between study day 30 and 365 will be terminated from the study. Safety labs will be collected at 7 days post last dose of study therapy medication. Adverse events data will be collected for 7 days post last dose of study therapy medication. Mortality will be assessed at 1 year and study closure. No other endpoints or labs will be collected post-retransplant.

7.9 Therapy Discontinuation

Should a study subject's therapy be discontinued prematurely for any reason and consent has not been withdrawn, all clinical and laboratory evaluations will continue. Safety labs will be collected 1 week post last dose of therapy discontinuation. All key endpoints will be evaluated and all randomized study subjects will continue to be followed as long as possible and included in the final analysis.

7.10 Final Study Visit

The planned final study exit visit (with the exception of late outcome assessment at study closure, see 7.11) will take place 12 months post-transplant +/- 2 weeks.

7.11 Study Closure

All-cause mortality, rejection episodes, graft loss and retransplantation, opportunistic infections (bacterial, fungal), need for dialysis, and post-transplant malignancies will be assessed until study closure (7 years from enrollment maximum).

Study coordinators will review medical records at study closure to obtain study closure assessments.

7.12 Total blood volume collected

Approximately 295.5 ml (~20 tablespoons) of blood will be collected specifically for study purposes in the preemptive therapy group and 176.5 ml (~12 tablespoons) in the prophylaxis group over the 12 months of study participation. This is depicted in Appendix B. Including the samples for clinical care and study specific samples, the blood volume collected over the study period is within accepted limits of blood collection.

7.13 Future Use of Stored Specimens

Some of the specimens obtained from study participants during this study will be stored indefinitely at the University of Washington and [name] Lab Fred Hutchinson Cancer Research Center and may be used in future research. These specimens will be labeled with a code number and not with the study participant's name. At the time of consent for study participation, the study participant or legal guardian will have the opportunity to either agree to have their specimens used in future research or decline to have their specimens used in future research. The study participant or legal guardian will indicate his/her preference by initialing the appropriate line or checking the appropriate box of the Consent Form in the section entitled, "Future Use of Specimens". Non-protocol designated, future testing of samples will be performed only on samples from study participants who have consented for future testing of samples.

A repository for residual samples will be established according to OHRP guidelines ensuring that code or other personally identifying links will not be distributed to future researchers. The specimens will be stored indefinitely at the University of Washington and [name] Lab Fred Hutchinson Cancer Research Center. Samples from study participants will be labeled and coded without study participant's identifiers. If the study participant or legal guardian has indicated in the signed consent form that he/she does not agree to allow the future use of specimens for research, then his/her specimens will be destroyed at the completion of the study.

8 STUDY PROCEDURES/EVALUATIONS

The study procedures and evaluations are summarized in Appendix A

8.1 Clinical Evaluations

8.1.1 Baseline demographics/medical history

Information will be recorded at the baseline study visit day 1 following randomization. Data collected will include basic demographics (information in compliance with the NIH Policy on Reporting Race and Ethnicity Data: Subjects in Clinical Research, Aug. 8, 2001 available at <http://grants.nih.gov/grants/guide/notice-files/NOT-OD-01-053.html>) gender; age, race; ethnicity. Subject weight will be recorded (weight recorded is the most recent weight obtained as standard care or obtained by the investigator). Also collected will be specific medical information including date of liver transplant, donor age and type (living or deceased), most recent standard of care MELD score prior to transplant, underlying liver diseases leading to transplant and co-morbid conditions (diabetes, cancer, cardiovascular disease, respiratory disease, renal disease). Specific baseline medications will be recorded including immunosuppressive agents, drugs with known hematologic toxicity, and any doses of antiviral agents. Standard of care clinical laboratory results, donor CMV serology, and study specific laboratory results will be recorded. All data will be abstracted from the medical records. Only current medical records from the transplant admission will be reviewed for baseline data collection. No past medical records will require review with the exception of confirmation of CMV serostatus with-in the allowable study window. No study specific physical examination will take place.

8.1.2 Adverse event assessment

All subjects will be assessed for adverse events throughout the administration of drug period plus 7 days. This is anticipated to be study day 1 through 107 for prophylaxis group subjects. Preemptive monitoring of AEs timelines will be individually determined by treatment for viremia detected during study days 1-100. Please see adverse event section for complete description of adverse event monitoring and reporting.

8.1.3 Neutropenia assessment

During active drug treatment, subjects will be monitored for neutropenia. Neutropenia with ANC \leq 1000/ μ L will be documented and reported as adverse events. Guidance for the evaluation and management of neutropenia are provided in the study manual of operations.

8.1.4 Assessment of CMV disease

CMV disease includes **CMV syndrome** or **tissue invasive CMV disease**. The following definition will be used for the study's primary efficacy analysis:

8.1.4.1 CMV syndrome

The subject has CMV infection (viremia) identified by a nucleic acid based assay [CMV DNA PCR, pp67mRNA or digene hybridization (non-amplification assay)] or antigenemia assay or viral culture

AND at least one of the following clinical/laboratory findings:

- Fever of $\geq 38^{\circ}\text{C}$ (100.4°F)
- Severe malaise
- Leukopenia defined as:

White blood cell (WBC) count of $<3,500/\mu\text{L}$ if the WBC count prior to the development of clinical symptoms is $\geq 4,000/\mu\text{L}$ **or**
WBC decrease of $> 20\%$ if the WBC count prior to the development of clinical symptoms is $< 4,000/\mu\text{L}$

- Atypical lymphocytosis of $\geq 5\%$
- Thrombocytopenia defined as:

Platelet count of $< 100,000/\mu\text{L}$ if the platelet count prior to the development of clinical symptoms is $\geq 115,000/\mu\text{L}$ **or**
Decrease of $> 20\%$ if the platelet count prior to the development of clinical symptoms is $< 115,000/\mu\text{L}$

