2 BACKGROUND INFORMATION AND SCIENTIFIC RATIONALE

2.1 Background

Cytomegalovirus (CMV) is a human herpes virus known to infect ~50-90% of the adults and is a major opportunistic pathogen in immunosuppressed populations such as transplant recipients. The term CMV infection indicates evidence of replicating virus as detected by laboratory testing in a blood sample (viremia). CMV disease on the other hand is defined by the presence of symptoms and signs attributable to this virus. CMV disease can manifest as viral syndrome with a flu-like illness or tissue invasive CMV disease and there are standardized criteria for their definitions in the literature (1, 2). Despite current preventive strategies, this virus continues to have a negative impact on outcomes in transplant recipients. The importance of preexisting immunity to CMV is evidenced by the substantially higher rates of infection and disease in subjects undergoing primary CMV infection (CMV naïve or seronegative recipients of CMV-seropositive allografts or R-/D+ recipients). In addition to overt disease, CMV-mediated immunomodulation can lead to indirect sequelae such as opportunistic infections, rejection, graft loss and reduced survival (3-5). Thus, strategies to optimally reduce the incidence and impact of CMV have the potential to significantly improve the outcome of transplantation.

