In the event that a preemptive subject has already received a dose of valganciclovir as standard care prior to randomization on study Day 1: study Day 1 will still remain the day of randomization and the dose given prior to randomization will not be considered a protocol deviation.

7. 5.3 Laboratory assessments

**7. 5.3.1 Drug safety labs (To be assessed during treatment period) all subjects- Study Days 7, 14, 21, 28, 42, 56, 70, 84, 98
(For study days 7, 14, 21, and 28 sample windows are +/-3 days. For study visits on study days: 42, 56, 70, 84, 98, samples windows are +/-7 days.)**

All subjects will have the following laboratory assessments completed at the transplant center while hospitalized. If discharged, laboratory assessments may be collected at routine care follow-up clinic appointments, at skilled nursing facilities, rehabilitation facilities, or outpatient laboratories.

The following laboratory assessments are anticipated to have been obtained as standard of care and will only be drawn specifically for the study if not completed as standard care within the allowable specified window.

Drug safety labs will be assessed and recorded for the entire treatment period in both the prophylaxis and preemptive group regardless whether the subject received valganciclovir/iv ganciclovir.

These labs will be continued at a bi-weekly interval (+/-7 days) in the preemptive subjects if receiving valganciclovir therapy after day 98 and continue until end of treatment.

- Hematology
 - Hemoglobin
 - Hematocrit %
 - Platelets
 - WBC with differential for absolute neutrophil calculation(ANC)
- Chemistry
 - Blood urea nitrogen
 - Serum creatinine with CrCl estimated
 - Total bilirubin
 - AST
 - ALT

ANC will be calculated at each safety lab visit. ANC < 1000/ μ L will be reported as an adverse event (please see protocol section 9.3).

CrCl (based on serum creatinine and most recent weight recorded as standard of care) will be estimated and monitored at each safety lab visit to assist in decisions related to recommended renal adjustments. (Please refer to MOP for calculation instruction for ANC and CrCl)

**7.5.3.2 CMV PCR surveillance monitoring – preemptive group only - Study days 7,14,21,28,35,42,49,56,63,70,77,84,91,98 (+/-3 days)
CMV PCR surveillance monitoring to be assessed in preemptive therapy subjects only**

Subjects in the preemptive group of the CAPSIL study will have CMV PCR serum sample obtained specifically for the study at study days:

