10.2 Responsibilities and Data Flow

The role of the EPC will be to evaluate and determine if the cases reported as having CMV disease by the investigators meet the protocol definition of CMV disease. In order to do so, the EPC will review all supporting clinical and laboratory data from such cases. The committee members will be blinded to the treatment allocation of all subjects in the study, including the subjects on which they are adjudicating. Subjects will be identified only with their study number. For the purposes of review, the following specific information will be provided to the EPC for the cases:

- Narrative summary that includes description of all signs and symptoms of the illness, and the reasons that the investigator diagnosed or suspected CMV disease.
- Type of CMV disease (viral syndrome or tissue invasive disease)
- Sites of CMV organ disease.
- Laboratory assay(s) that detected CMV disease
- Biopsy findings (if applicable)
- Other relevant laboratory, imaging studies or diagnostic procedures
- Outcome of disease and treatment employed.

The coordinating center will provide the required documents to the EPC. The EPC event adjudication will occur prior to interim analysis and prior to close out. It is anticipated that there will be approximately 30 CMV disease events to be reviewed.

The EPC will provide the coordinating center and the DMID with the conclusion for all cases that it has reviewed and whether the event meets the protocol definition of CMV disease (yes or no). When a unanimous decision cannot be made on the adjudication of the case by the three committee members, a vote will be taken and the majority vote will hold.

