- Pulmonary: Acute lung injury, respiratory distress syndrome, aspiration, asthma, atelectasis, mucus plugging, respiratory failure, dyspnea, hypoxia, pneumonia, pleural effusion, pneumothorax, pulmonary edema, sinusitis, need for mechanical ventilation, intubation or reintubation, chest tube insertion, pleural effusion, embolism, pulmonary hypertension
- Electrolyte and metabolic: Acidosis or alkalosis, low albumin, dehydration, gout, elevated liver function tests (bilirubin and liver enzymes), increase or decrease in the level of

sodium, potassium, blood urea nitrogen, creatinine, glucose, calcium, magnesium, phosphate, uric acid, cholesterol, lipids, iron

- Hematologic: Anemia, blood loss, prolonged PT or PTT, abnormalities in coagulation (DIC), hematoma, hemorrhage, bleeding, venous thrombosis, thrombocytopenia/thrombocytosis, leukopenia/leukocytosis, thrombotic thrombocytopenic purpura, hemolytic uremic syndrome, pancytopenia
- Cardiac: Arrhythmias (atrial flutter, atrial fibrillation, ventricular fibrillation), prolonged QT interval, QRS or ST segment abnormal, tachycardia, bradycardia, torsade de pointes, hypertension, hypotension, pulmonary hypertension, myocardial ischemia or infarction, syncope, postural hypotension, phlebitis, thrombosis, myocardial hypertrophy, cardiomyopathy, anaphylaxis, shock, anaphylactoid reaction, angioedema, arterial dissection
- Renal: Acute renal failure, albuminuria, nephropathy, hematuria, renal tubular necrosis, interstitial nephritis, nephropathy
- Genitourinary: Bladder spasm, dysuria, nocturia, incontinence, urinary frequency, urinary retention, hemorrhagic cystitis
- Malignancies: Lymphoproliferative disorder, skin neoplasm, melanoma, hepatocellular carcinoma, hematologic or solid tumor.
- Dermatologic: Edema at anybody site, rash (petechiae, purpura, spider angioma), ecchymosis, bruising, flushing, cellulitis, dermatitis, Stevens-Johnson syndrome, toxic epidermal necrolysis, decubitus ulcer, photosensitivity, skin ulcer, wound healing impaired.

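### The CMV syndrome definition does not tie the clinical finding to CMV or to the date of viremia, so case ascertainment can differ by arm while only the preemptive arm has weekly PCR

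*Combined protocol and SAP*

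**What the plan says.** Section 8.1.4 introduces the definition with "The following definition will be used for the study's primary efficacy analysis". Two routes lead to a case: tissue-invasive disease and CMV syndrome.

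For CMV syndrome, section 8.1.4.1 has two limbs. The first is "The subject has CMV infection (viremia) identified by a nucleic acid based assay", or antigenemia or culture, with no viral load threshold. The second is "AND at least one of the following clinical/laboratory findings": fever, severe malaise, a WBC fall, atypical lymphocytosis or a platelet fall. Section 2.1 is stricter. It separates infection (viremia) from disease, which is "defined by the presence of symptoms and signs attributable to this virus".

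On testing, section 7.5.3.2 states "CMV PCR surveillance monitoring to be assessed in preemptive therapy subjects only", on study days 7 to 98 and longer if therapy continues. Sections 7.6.4 and 8.1.4.3 provide a central PCR in either arm when disease is suspected, up to 12 months. Sections 6.2.1 and 6.2.2.2 start valganciclovir in the preemptive arm on viremia at any level.

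On adjudication, the EPC's task in section 10.2 is to "determine if the cases reported as having CMV disease by the investigators meet the protocol definition of CMV disease". Section 12.5.1 also admits investigator-determined cases that do not meet the definition.

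**The concern.** Preemptive therapy lets viremia occur by design, so in that arm the second limb does most of the work of separating infection from disease. That limb is non-specific. Appendix C lists fever and "thrombocytopenia/thrombocytosis, leukopenia/leukocytosis" as expected events, and section 2.3.1.2 names leukopenia and neutropenia as the most common ganciclovir effects. Read literally, a preemptive subject with surveillance viremia and a drug-related WBC fall meets the primary endpoint. A prophylaxis subject with the same fall meets it only if someone suspects CMV and sends a PCR that is positive.

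Extra reported cases would raise the preemptive rate. They would dilute a true preemptive benefit, weaken the non-inferiority assessment, and could suggest harm where true disease is equal. If unblinded investigators instead decline to report viremia that is already being treated, the error runs the other way. Either way, part of the primary result would depend on open-label discretion rather than on the written rule.

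**Working it through.** **The plan's own figure.** Section 12.1 assumes 20% versus 5% and gives 80 per group with 20 events.
- HR = ln(0.95)/ln(0.80) = 0.230.
- Events (Freedman) = (1.960 + 0.842)² × [(1 + 0.230)/(1 − 0.230)]² = 20.02.
- Per group = 20.02/(0.20 + 0.05) = 80.07, so the plan's figure reproduces.
- Exact two-sided Fisher power at 80 per group is 79.3%. The unstratified chi-square by exact enumeration gives 85%.
- Expected preemptive cases: 80 × 0.05 = 4.

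**Sensitivity to a few extra cases.** Prophylaxis is held at 20% and the excess is assumed. Fisher power at 80 (88) per group is 79% (84%) with no excess, 61% (67%) at +2 points and 35% (39%) at +5 points. At 80 per group, +2 points is about 2 subjects and +5 points is 4.

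**Link to the definition.** Let d be the true disease rate, v the proportion of preemptive subjects found viremic, and q the chance that a viremic subject without true disease has a qualifying *and reported* non-CMV finding. Then

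observed preemptive rate = d + (v − d) × q.

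The documents give neither v nor q. I take v = 60%, add no cases in prophylaxis, and use the two-sided chi-square at 0.05 with 80 per arm.

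Planned truth, 20% versus d = 5%. For example, q = 10% gives 0.05 + 0.55 × 0.10 = 0.105.

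| q | Observed preemptive rate | Power |
|---|---|---|
| 0 | 5.0% | 85% |
| 1% | 5.6% | 81% |
| 2% | 6.1% | 77% |
| 5% | 7.8% | 62% |
| 10% | 10.5% | 38% |
| 20% | 16.0% | 10% |

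Over v = 40% to 80%, power runs from 71% to 53% at q = 5% and from 55% to 25% at q = 10%.

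True equality, 10% versus d = 10%:

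| q | Observed preemptive rate | Rejection against preemptive therapy |
|---|---|---|
| 0 | 10.0% | 2.4% |
| 5% | 12.5% | 7% |
| 10% | 15.0% | 15% |
| 25% | 22.5% | 58% |

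At q = 25%, the last figure is 28% if v = 40% and 83% if v = 80%.

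**Non-inferiority.** Take 80% versus 89% true success, a 5% margin and one-sided 0.05. Power = Φ[(0.05 + p − 0.80)/SE − 1.645], with SE² = 0.80 × 0.20/80 + p(1 − p)/80. This gives 79% at p = 0.89, 66% at 0.87 (+2 points) and 44% at 0.84 (+5 points).

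**The case against.** A reader might infer that the case rule follows the surveillance schedule rather than disease, and that misclassified cases fall almost wholly in the preemptive arm. The documents do not support that, for five reasons.

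- **No case is counted automatically.** The EPC sees only what a site investigator reports as CMV disease, with the reasons for the diagnosis (sections 10.1 and 10.2). Reporting can add preemptive cases or withhold them.
- **Both arms get a PCR on suspicion**, local CMV testing is allowed, and safety blood counts follow the same schedule in both arms (section 7.5.3.1).
- **The asymmetry is limited in time and partly real.** Surveillance ends about day 98 unless therapy continues, and later detection is mainly symptom-driven in both arms. Section 2.2 says prophylaxis almost completely suppresses replication, so part of the viremia gap is a true effect. Adding no cases in prophylaxis is a worst-case input.
- **Part of the remedy exists.** Section 12.6.1.1 plans adjudicated disease at 3 and 12 months, with separate subsets for syndrome and tissue-invasive disease.
- **Large q is not documented.** Section 2.3.1.2.6 gives neutropenia of 1.2% at day 21 on 900 mg twice daily, and 2% within 4 weeks on prophylaxis. Neutropenia is narrower than the WBC criterion and is only one of several qualifying findings, so these figures are not q. They do caution against emphasising the bottom rows of the tables.

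It can also be argued that the WBC and platelet criteria presuppose symptoms, because they compare with counts before symptoms developed. That wording sets a baseline. It does not make symptoms a condition, since one listed finding suffices. The ambiguity is a further reason to clarify.

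Two gaps remain. The work-up in section 8.1.4.3 addresses other infections, not drug-related cytopenia, and is not part of the case definition. EPC blinding does not help either, because the committee applies the same definition and never sees an unreported episode.

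**Conclusion.** The concern holds as a gap in the primary case definition. Section 8.1.4.1 drops the attribution that section 2.1 makes part of disease and sets no time link, so ascertainment can differ by arm at about days 7 to 98. The EPC process does not correct this.

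Direction and size are not fixed by the documents. With 60% viremia assumed, the loss of power is modest at q = 1% to 2% (85% to 81% or 77%) and serious at 5% to 10% (62% or 38%). A false finding against preemptive therapy under equality is 7% at q = 5% and 15% at q = 10%. It reaches 58% only at q = 25%, for which the documents give no support. The firmest point needs no assumption about viremia: with 4 preemptive cases expected in 80, about 2 extra subjects take Fisher power from 79% to 61%. The definition should be tightened, but the gap does not invalidate the design.

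**What to change.** 1. In section 8.1.4.1, require that the qualifying finding begin within a pre-specified window of the positive CMV test. Also require that the blinded EPC judge it attributable to CMV rather than to another documented cause, including drug-related cytopenia. The sponsor sets the window; the documents offer no basis for a particular length. Mirror both criteria in section 10.2.
2. In section 12.5.6, add a repeat of the primary analysis on tissue-invasive disease plus syndrome with fever or severe malaise. Exclude cases that qualify only on WBC, platelets or atypical lymphocytes. Report laboratory-only cases by arm, and whether the qualifying PCR was a surveillance or a symptom-triggered sample.
3. Cite the tissue-invasive subset of section 12.6.1.1 as supportive of the primary analysis. No new analysis is needed.

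Cost: wording, one EPC criterion and one repeat analysis, using blood counts, PCR dates and recorded hematotoxic drugs (days 1 to 100) that are already collected. The downsides are somewhat fewer events and a little more EPC judgment. Case summaries would need care so that PCR and drug details do not reveal the arm. Unequal PCR ascertainment of findings that truly are due to CMV would remain and should be stated as a limitation.
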